## **10.2 Sample size and analysis of the primary efficacy endpoint**

At a survey conducted in April 2019, 5363 of the 5887 (91%) children enrolled in the first phase of the trial were contactable, an annual loss of about 5%. Assuming that this rate of attrition continues for a further year and that a similar proportion of families do not consent for their child to join the extension study, it is likely that approximately 4,800 children will enter the extension study.

The primary analyses will cover the entire study period, ie. the initial three years of the study and the two year extension period. The entire study period is defined as the time from enrolment in June 2017 until the end of the study year in which the child reaches five years of age and is no longer eligible for SMC, i.e. between 5 and 20 months of age (depending upon the exact age at first vaccination) and 60-71 months of age (depending upon the timing of the child's fifth birthday in relation to the SMC schedule). On the basis of date of enrolment, the exit dates above, and losses to follow-up as described above, we estimate that there will be approximately 20,625 person-years of follow-up during the entire study period: 6875 person-years per study group (i.e. an average of 3.5 person-years per child originally recruited).

The primary end-point for the trial is the incidence of clinical episodes of malaria. Based on data from the first two years of the ongoing study, we assume that the incidence of malaria will be 200 cases per 1000 children per year over the entire study period. Based on this assumption, the study will have 90% power to detect a 12.0% or greater relative difference (absolute difference: 24 cases per 1000 child-years) between the RTS,S/AS01E + SMC and the RTS,S/AS01E alone or SMC alone groups, through a standard superiority comparison.

The study will also have 90% power using a two sided 95% confidence interval to exclude a 17.5% relative difference (absolute difference: 35 cases per 1000 child-years) in incidence of clinical malaria between children in the RTS,S/AS01E alone or SMC alone group, using a non-inferiority design, over the entire study period. To determine the level of confidence with which this margin can be excluded, we will also calculate two sided 90% and 99% confidence intervals.

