There will be approximately 4,100 child-years of observation in the year following the third booster; 1367 child-years in each study group. Assuming the incidence of clinical episodes of malaria remains at about 200 episodes per 1,000 children per year during this period, the study will have 90% power, through a standard superiority comparison, to detect a 25.9% or greater relative difference (absolute difference: 52 cases per 1000 child-years) between the RTS,S/AS01E + SMC and the RTS,S/AS01E alone or SMC alone group. In the same period, the study will have 90% power, using a two sided 95% confidence interval, to exclude a 39.2% relative difference (absolute difference: 78 cases per 1000 child-years) in the incidence of clinical malaria between children in the RTS,S/AS01E alone or SMC alone group, using a non-inferiority design.

A similar analysis will be undertaken for the final year of the study following administration of a fourth booster dose of the RTS,S/AS01E or comparator vaccine but study power will be reduced because slightly more than half of the children enrolled (3860/5920) will not be eligible for SMC in 2021-22, and thus will not contribute further events nor person-time at risk to the study period.

Both intention-to-treat and per-protocol analyses will be undertaken. Children who received any dose of SMC or vaccine will be included in the intention to treat analysis. Children who received all scheduled doses of SMC, or who were treatment for a clinical episode of malaria at a time when SMC would have been given, or all scheduled doses of vaccine will be included in the per protocol analysis for each year of the study. Results obtained in Burkina Faso and Mali will be analysed separately. Additional sub-analyses will include analysis by age, gender, and bed net use during the transmission season, as determined by the history obtained at the cross-sectional surveys.

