SMC is the standard of care in both Burkina Faso and Mali. Consequently, if it is not possible to establish that RTS,S/AS01E given alone is as effective as SMC in preventing clinical episodes of malaria, it would not be justifiable to continue with the RTS,S/AS01E alone group in the trial. The efficacy of SMC (against placebo or no SMC) has been well established in clinical trials and, more recently, through case control studies in Mali and Burkina Faso. Efficacy of SMC against no SMC was about 50% over the whole year, although higher during the four months of the malaria transmission season. The non-inferiority margin is the largest reduction in this efficacy that would be considered acceptable if RTSS/AS01 was to replace SMC. A reduction in efficacy from 50% to 40%, which might be considered acceptable, translates to a 20% greater incidence in the RTSS/AS01-alone arm (the comparator) compared to the SMC-alone arm. This reduction in efficacy might be considered acceptable taking into account the potential advantages of RTS,S/AS01E over SMC in terms of ease of delivery and hence the likelihood of being able to sustain high levels of coverage. We have, therefore, chosen a margin of 20% in clinical incidence between the RTS,S/AS01E alone and SMC alone groups as the margin on which a decision will be based (this is slightly higher than the 16.1% margin used in the protocol to define the study's power to measure this end-point).

If the incidence rate ratio RTS,S/AS01E alone: SMC alone can be shown to be less than 1.20 then we can conclude that RTS,S alone is non-inferior to SMC alone. Two-sided 99%, 95% and 90% confidence intervals for the rate ratio will indicate the degree of confidence with which the margin of 1.20 (relative increase of 20%) can be excluded. Examples of how the confidence intervals might be interpreted are shown in Figure 1.

Figure 1. Interpretation of the possible findings in the comparison between RTS,S/AS01E and SMC.

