**Strategy to address multiplicity**

Hypothesis testing for analyses of the primary outcome will follow the closed testing procedure, whereby there is initially a test of the null hypothesis that the incidence in the three groups is the same. If this is rejected at the 5% level, pairwise comparisons will be done also using a 5% significance level. Pairwise comparisons can be considered statistically significant only if the overall null hypothesis is rejected. P-values and 95% confidence intervals will be presented.

For the non-inferiority comparison of the primary outcome described above, we will calculate two-sided 95% confidence intervals, equivalent to the use of a one-sided significance level of 2.5%, as is recommended (4). To illustrate the level of confidence with which non-inferiority can be declared, we will plot the point estimate for the hazard ratio with two-sided 90, 95 and 99% confidence intervals, and the non-inferiority margin (a hazard ratio of 1.2, which would reflect 20% higher incidence of clinical malaria in children in the RTS,S/AS01E alone group, relative to the SMC alone group).

For secondary outcomes, we will present 95% confidence intervals, without adjustment for multiplicity, stating that no adjustment was made.

For safety outcomes, we will present p-values and 95% confidence intervals, without adjustment for multiplicity.

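### Protocol 10.2 calls a 17.5% excludable difference the non-inferiority margin, never names the 20% decision margin, and its 17.5% and 39.2% do not follow from its own inputs

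*Combined protocol and SAP*

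**What the plan says.** **Protocol 10.2, whole study period.** For RTS,S alone against SMC alone, the sample is credited with 90% power, judged by the 95% interval, "to exclude a 17.5% relative difference (absolute difference: 35 cases per 1000 child-years) in incidence of clinical malaria". The next sentence opens "To determine the level of confidence with which this margin can be excluded" and adds two-sided 90% and 99% intervals. The only figure it can refer back to is 17.5%. The inputs are "6875 person-years per study group" and 200 cases per 1000 children per year.

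**Protocol 10.2, year after the third booster.** With 1,367 child-years per group and the same incidence, the study has 90% power "to exclude a 39.2% relative difference". No decision margin is named.

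**Protocol Appendix 1, efficacy decisions.** A loss of SMC efficacy from 50% to 40% is converted to 20% higher incidence, and 20% is chosen as the margin for the decision. The text adds that "this is slightly higher than the 16.1% margin used in the protocol" and says that the 16.1% served to define power.

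**SAP, illustrative sample size calculations.** The same 50%-to-40% reasoning gives 20%. The sentence about 90% and 99% intervals reappears, now referring to 20%. The SAP adds that the study could reject a smaller margin but that 20% is the largest difference regarded as unimportant.

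**SAP, Strategy to address multiplicity.** The 90%, 95% and 99% intervals will be plotted with "the non-inferiority margin (a hazard ratio of 1.2, which would reflect 20% higher incidence of clinical malaria" in the RTS,S alone group.

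**The concern.** The protocol section that defines the primary analysis should state the criterion for a primary objective. A reader of 10.2 finds only 17.5%, described as the margin. A reader of the SAP finds 1.20 attached to the same display of intervals. An upper limit of 1.19 would then fail one document and pass the other, and a non-inferiority claim resting on it could be challenged.

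The figures in 10.2 also tell the reader how precise the trial is. If they cannot be obtained from the inputs printed beside them, the reader cannot tell what was assumed about variance.

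The SAP plans hypothesis tests for the whole period (A), year 4 (B) and year 5 (C), and bases the extension's primary objective on the final two years. Yet neither document gives power at 1.20 for B or C.

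**Working it through.** **Inputs.** Protocol 10.2: 6,875 child-years per group (whole period), 1,367 (year 4), 0.200 cases per child-year, 90% power, two-sided 95% interval. Expected events per group: E = 6,875 × 0.200 = 1,375 and E = 1,367 × 0.200 = 273.4. The true ratio is taken as 1, as the SAP states for its own calculation. z(0.975) + z(0.90) = 1.960 + 1.282 = 3.2415.

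**1. Superiority figures, as a check on method.** For relative reduction d, power = Φ[0.2d / √((0.2 + 0.2(1 − d)) / PY) − 1.96].
- d = 0.120, PY = 6,875: 90.1%.
- d = 0.259, PY = 1,367: 90.1%.

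Both printed superiority figures follow from the stated per-group person-years.

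**2. Non-inferiority figures.** Excludable difference = 3.2415 × √(V/E), where V = 2 for two independent Poisson arms. The log-scale form is exp(that) − 1.

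| Period | E | V = 2, linear | V = 2, log | V = 4, linear | Printed |
|---|---|---|---|---|---|
| Whole period | 1,375 | 12.4% | 13.2% | 17.5% | 17.5% |
| Year 4 | 273.4 | 27.7% | 31.9% | 39.2% | 39.2% |

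The printed values return only with V = 4, that is, with person-years halved or variance doubled. The rebound figures in protocol 10.3.4 behave the same way. With 800 × 0.600 = 480 events per group and V = 4, the results are 29.6% at 90% power and 25.6% at 80%, as printed. The non-inferiority figures therefore share a factor of two that the superiority figures lack, and 10.2 does not mention it.

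**3. The 16.1%.** At 200 per 1000, excluding 16.1% with 90% power needs 2 × 3.2415² / 0.161² / 0.2 ≈ 4,050 child-years per group on the linear scale, about 4,715 on the log scale, or about 8,107 with V = 4. None of these is 6,875. ln(1.175) = 0.161, which may be coincidence.

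**4. The band where the readings disagree.** With E = 1,375 and V = 2, SE = √(2/1,375) = 0.0381. The upper limit equals 1.175 at an estimated ratio of 1.175 × exp(−1.96 × 0.0381) = 1.090, and equals 1.20 at 1.114. The chance of landing between them depends on the true ratio:

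| True ratio | V = 2 | Doubled variance |
|---|---|---|
| 1.00 | 0.9% | 7% |
| 1.05 | 9.6% | 15% |
| 1.10 | 22% | 14% |

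**5. Power at 1.20, equal arms.** Power = Φ[ln(1.20) / √(V/E) − 1.96], with ln(1.20) = 0.1823.

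| Period | E | V = 2 | V = 4 |
|---|---|---|---|
| A, 200 per 1000 | 1,375 | 99.8% | 92% |
| Year 4, 200 per 1000 | 273.4 | 57% | 33% |
| Year 4, 305 per 1000 | 416.9 | 75% | 46% |

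The 305 is the SMC-alone rate over the first three years, from the SAP's superiority paragraph.

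Year 5 person-time is not stated, so it must be assumed. From the 3,860 of 5,920 children that 10.2 counts as ineligible, (5,920 − 3,860)/3 ≈ 687 children per group remain before attrition. One child-year each gives E = 137.4 and power of about 33% (V = 2). An assumed range of 541 to 780 child-years per group gives 27% to 36%.

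**The case against.** The strongest reply is that the documents hold only one decision margin. Every place that states a decision rule or its rationale (both efficacy decision passages of Appendix 1, and the SAP's sample size and multiplicity sections) uses 20%. The 17.5% and 39.2% sit in power statements. Section 10.3.4 gives two such figures for a single comparison at two power levels, so the form reports what the sample can exclude. Protocol 10.1 leaves detailed procedures to the SAP, which is explicit. This stands. The pass/fail conflict exists only if the back-reference in 10.2 is taken literally.

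Two stronger readings are tempting and should not be drawn:

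- **Three rival margins of 16.1%, 17.5% and 20%.** Appendix 1 labels 16.1% a power figure in the sentence that chooses 20%, so Appendix 1 and the SAP cannot reach opposite verdicts on one limit. The protocol it cites may be that of the original trial, which is not available here, so the mismatch with 10.2 does not prove an error.
- **The looser 20% was picked after the three-year results.** The SAP does cite those results. But Appendix 1 already sets 20%, with the same efficacy reasoning, as a plan for a preliminary review that it treats as still to come. The SAP carries that margin forward.

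On size, the disagreement band is unlikely to be hit if the arms are truly equal and variance is Poisson. A doubled variance could be a deliberate allowance for repeated episodes within children, for which the SAP plans robust standard errors. If so, it should be stated. It would also need reconciling with the superiority figures, which carry no such allowance.

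**Conclusion.** The concern holds as a defect of wording and of stated figures in protocol 10.2. It is worth correcting because it touches the criterion of a primary objective.

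- Section 10.2 presents 17.5% as the margin and omits 20%. Literal reading conflicts with the SAP only for upper 95% limits from 1.175 to 1.20.
- The 17.5% and 39.2% are excludable differences and are overstated for the inputs given: about 12.4–13.2% and 27.7–31.9% under equal arms, Poisson counts and 200 per 1000. The error is conservative, since the stated inputs support better precision than claimed.
- The 20% margin is well supported over the whole period (99.8%, or 92% with doubled variance), which agrees with the SAP's claim of more than 90% power. It is not well supported in single years: about 57% for year 4 at 200 per 1000, about 75% at 305, and lower for year 5 under any of the assumed person-times. Within-child clustering beyond Poisson would reduce these values.

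The documents support neither a contest between three decision margins nor a margin chosen after the results.

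**What to change.** In protocol 10.2:

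1. State that the single non-inferiority margin is a ratio of 1.20 (20% higher incidence, RTS,S alone against SMC alone), and tie the 90%, 95% and 99% intervals to it, as in the SAP.
2. Relabel 17.5% and 39.2% as differences excludable with 90% power. Either recompute them from the stated person-years or state the variance inflation used and why the superiority figures omit it. Treat the rebound figures in 10.3.4 the same way.

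In Appendix 1, give the source of the 16.1% or correct it.

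In the SAP, state power at 1.20 for each period tested (A, B and C), with the incidence, person-time and variance assumed. Year 5 person-time has to be supplied.

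The cost is wording and a short recalculation. The margin, design and data collection do not change. The drawback is that the low single-year power becomes visible; the text should then say that the non-inferiority conclusion rests on the whole intervention period.

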## DECISIONS MADE ON THE GROUNDS OF SAFETY

- SMC alone is standard of care and so will act as the baseline for safety assessments (SMC has been shown in several large studies to be very safe). Thus, the trial's DSMB will be asked to consider the safety of children in the SMC plus RTS,S/AS01E and the RTS,S/AS01E alone groups in relation to findings in the SMC alone group based on an analysis of deaths overall, deaths attributed to malaria, SAEs overall and SAEs attributed to malaria. If there is a significant increase in the overall incidence of serious adverse events, primarily deaths or hospital admissions, not due to trauma or elective surgery or in the incidence of SAEs due to severe malaria in one of the RTS,S/AS01E groups compared with the SMC alone

group, the DSMB may recommend that the affected group should not continue in the trial. If there is a significant increase in both RTS,S/AS01E groups the DSMB may recommend that the trial should not be extended. Definition of what would be considered to be sufficient evidence of risk in the groups receiving RTS,S/AS01E will be a decision for the DSMB but, in such circumstances, a difference in the incidence of serious adverse events between groups that reaches a statistical significance of  $P = 0.01$  or less is usually considered to be one potential reason for dropping a trial group. These data will also be made available to GSK.

[figure not shown]
## **SEROLOGY**

Serological findings will not be available in time for the preliminary evaluation.

## **CONCLUSIONS**

Deciding on whether to continue the RTS,S/AS01E + SMC trial and, if so, whether this should be with all three arms will require some subjective decisions based on balancing the potential risks and benefits of doing so. However, this document should help to provide a framework that will aid in making these decisions and a potential pathway is shown in Figure 2.

Figure 2. Decision pathway

## Appendix 2

### Definitions of adverse and serious adverse events and reporting schedule

#### A. Definition of an adverse event, adverse events of special interest, and serious adverse event

##### A.1 Definition of adverse event (AE)

An adverse event (AE) is defined as any clinical symptom or sign that occurs in a study child after administration of the study vaccine or drugs that may or may not have a causal relationship with the study drugs. Examples of an AE include -

(1) Occurrence of symptom such as fever, vomiting or diarrhoea in a child who did not have these symptoms prior to the administration of drugs; (2) Unexpected worsening of an existing condition.

##### A.2 Definition of Adverse Events of Special Interest

AEs of specific interest for safety monitoring include all seizures occurring within 30 days post-vaccination, meningitis and pIMDs and will be recorded in the CRF.

Meningitis cases: For the further evaluation of the safety signal of meningitis in the investigational vaccine groups all cases of meningitis occurring during the study will be reported as a SAE.

pIMDs are a subset of AEs that include autoimmune diseases and other inflammatory and/or neurologic disorders of interest which may or may not have an autoimmune etiology. AEs that need to be recorded and reported as pIMDs include those listed in Table A.

Table A. List of Potential Immune-mediated Diseases:

| Neuroinflammatory disorders  | Musculoskeletal disorders  | Skin disorders  |
|--|--|---|
| 
 
• Cranial nerve disorders, including paralyses/paresis (e.g. Bell's palsy)
 
• Optic neuritis
 
• Multiple sclerosis
 
• Transverse myelitis
 
• Guillain-Barré syndrome, including Miller Fisher syndrome and other variants
 
• Acute disseminated encephalomyelitis, including site specific variants: e.g. non-infectious encephalitis, encephalomyelitis, myelitis, myeloradiculoneuritis
 
• Myasthenia gravis, including Lambert-Eaton myasthenic syndrome
 
• Immune-mediated peripheral neuropathies and plexopathies,
 
 | 
 
• Systemic lupus erythematosus and associated conditions
 
• Systemic scleroderma (Systemic sclerosis), including diffuse systemic form and CREST syndrome
 
• Idiopathic inflammatory myopathies, including dermatomyositis
 
• Polymyositis
 
• Antisynthetase syndrome
 
• Rheumatoid arthritis, and associated conditions including juvenile chronic arthritis and Still's disease
 
• Polymyalgia rheumatica
 
• Spondyloarthritis, including ankylosing spondylitis, reactive arthritis (Reiter's
 
 | 
 
• Psoriasis
 
• Vitiligo
 
• Erythema nodosum
 
• Autoimmune bullous skin diseases (including pemphigus, pemphigoid and dermatitis herpetiformis)
 
• Alopecia areata
 
• Lichen planus
 
• Sweet's syndrome
 
• Localised Scleroderma (Morphea)
 
 |

|  |  |  |
|--|--|--|
| 
 
(including chronic inflammatory demyelinating polyneuropathy, multifocal motor neuropathy and polyneuropathies associated with monoclonal gammopathy).
 
• Narcolepsy
 
   | 
Syndrome) and undifferentiated spondyloarthritis
 
 
• Psoriatic arthropathy
 
• Relapsing polychondritis
 
• Mixed connective tissue disorder
 
  |  |
| 
Vasculitides
 
 
• Large vessels vasculitis including: giant cell arteritis such as Takayasu's arteritis and temporal arteritis.
 
• Medium sized and/or small vessels vasculitis including: polyarteritis nodosa, Kawasaki's disease, microscopic polyangiitis, Wegener's granulomatosis, Churg–Strauss syndrome (allergic granulomatous angiitis), Buerger's disease (thromboangiitis obliterans), necrotizing vasculitis and anti-neutrophil cytoplasmic antibody (ANCA) positive vasculitis (type unspecified), Henoch-Schonlein purpura, Behcet's syndrome, leukocytoclastic vasculitis.
 
 | 
Blood disorders
 
 
• Autoimmune hemolytic anemia
 
• Autoimmune thrombocytopenia
 
• Antiphospholipid syndrome
 
• Pernicious anemia
 
• Autoimmune aplastic anaemia
 
• Autoimmune neutropenia
 
• Autoimmune pancytopenia
 
 | 
Others
 
 
• Autoimmune glomerulonephritis (including IgA nephropathy, glomerulonephritis rapidly progressive, membranous glomerulonephritis, membranoproliferative glomerulonephritis, and mesangioproliferative glomerulonephritis)
 
• Ocular autoimmune diseases (including autoimmune uveitis and autoimmune retinopathy)
 
• Autoimmune myocarditis/cardiomyopathySarcoidosis
 
• Stevens-Johnson syndrome
 
• Sjögren's syndrome
 
• Idiopathic pulmonary fibrosis
 
• Goodpasture syndrome
 
• Raynaud's phenomenon
 
 |
| 
Liver disorders
 
 
• Autoimmune hepatitis
 
• Primary biliary cirrhosis
 
• Primary sclerosing cholangitis
 
• Autoimmune cholangitis
 
  | 
Gastrointestinal disorders
 
 
• Inflammatory Bowel disease, including Crohn's disease, ulcerative colitis, microscopic colitis, ulcerative proctitis
 
• Celiac disease
 
• Autoimmune pancreatitis
 
   | 
Endocrine disorders
 
 
• Autoimmune thyroiditis (including Hashimoto thyroiditis)
 
• Grave's or Basedow's disease
 
• Diabetes mellitus type I
 
• Addison's disease
 
• Polyglandular autoimmune syndrome
 
• Autoimmune hypophysitis
 
  |

A serious adverse event is any clinical condition that fulfils at least one of the following criteria:

- (1) Results in death.
- (2) Results in admission to hospital.
- (3) Is life-threatening (the child was at risk of death at the time of the adverse event).
- (4) Results in disability/incapacity.

